Postoperative hypoxemia it is a strong indicator of patient instability, compromises wound healing and promotes other serious complications, including brain dysfunction, dysrhythmias and myocardial ischemia. Prolonged hypoxic episodes have been reported to be common in hospitalized patients recovering from non-cardiac surgery: up to 37% of patients had at least one episode of oxygen saturation < 90% lasting more than one hour while 3% had saturations <80% for at least 30 minutes.

Postsurgical patients at-risk of developing cardiopulmonary complications could benefit from both preventive interventions and more intensive postsurgical monitoring. Up to 84% of in-hospital cardiopulmonary arrest events are preceded by prolonged periods of physiological and clinical instability. Early intervention of clinically unstable patients by a medical emergency team significantly reduces the incidence of, and mortality from, unexpected cardiac arrest in hospital. A significant decrease in the number of cases of respiratory failure, stroke, severe sepsis, and acute renal failure was also shown after the implementation of a medical emergency team in an Australian study. In 2007, the UK National Institute for Health and Clinical Excellence recommended the use of physiological track and trigger systems to monitor adult patients in acute hospital settings: these systems, also known as Early Warning Scores (EWS), are based on the monitoring of patients' basic physiological observations such as pulse rate, SpO2, blood pressure, respiration rate, temperature and conscious level and are used to identify patients at risk of respiratory failure, cardiac arrest and death. A systematic review has reported that EWS have a strong predictive value for the occurrence of cardiac arrest and death within 48 hours of measurement. EWS has been demonstrated to be effective in predicting clinical deterioration that may lead to a cardiac arrest also in patients in wards that are poorly equipped to detect rapid patient deterioration. National EWS (NEWS), based upon common vital signs such as temperature, respiratory rate, heart rate, systolic blood pressure, nursing assessments of consciousness level of the patient, SpO2 and use of supplemental oxygen is one of the most frequently utilized.

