Respiratory compromise (RC) is a state in which there is a high likelihood of decompensation into respiratory depression, respiratory failure or death, but in which specific interventions (enhanced monitoring and/or therapies) might prevent or mitigate decompensation. Patients with RC have up to a two-fold increase in mortality following delayed medical emergency team activation. Detecting a patient's declining RC status before progression to respiratory depression in patients continuously monitored in the general ward could allow earlier intervention, thus potentially decreasing adverse outcomes.

Due to possibly improved patient safety, continuous SpO2 and capnography monitoring combined with automated decision support tools to determine potential or established patient critical illness are starting to have an important role also outside ICU. Current standard of care for respiratory monitoring of high risk hospital ward patients, such as those receiving opioid therapy, is intermittent documentation of SpO2 value (e.g. spot checks performed at 4 to 6 hours intervals). Respiratory rate (RR) is often determined by clinician assessment though manual inaccurate respiration counts.

Growing evidence supports the use of capnography for earlier and more reliable warnings of potential RC in postoperative patients in the general ward, compared with pulse oximetry. Capnography monitoring has also been associated with in-hospital mortality in emergency department patients with cardiac arrest and suspected sepsis across a range of disease severity.

There are no data on the real incidence and severity of potential RC markers and their correlation with cardiopulmonary or other complications in European postsurgical patients. A pilot study on this topic could be useful to collect information on the utility of continuous SpO2 and capnography monitoring in this setting and to develop future clinical evidence. This study may also provide the data needed to evaluate certain health-economic outcomes associated with introduction of continuous monitoring in the general ward setting.

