#### 4.1.2. Secondary Objectives and Endpoints

The study secondary objectives are the followings:

1. To compare the two study Phases (see Section 5) in terms of primary endpoint incidence.
2. To compare the two study Phases in terms of respiratory AEs and SAE incidence, number of ICU transfers and related length of stay, Code blues and RRT responses.
3. To evaluate the impact of introducing continuous monitoring devices connected to a remote monitoring platform on the clinical workflow, defined as the rate of clinical early interventions performed by nursing staff to prevent a potential AE (e.g. patient stimulation, Jaw thrust maneuver, oxygen administration started or increased, medication change, etc.).

4. To evaluate the impact of introducing continuous monitoring devices connected to a remote monitoring platform on clinical staff workflow, defined as clinical staffs' satisfaction related to the monitoring system.
5. To characterize the predictive values of etCO2, RR, SpO2, plethysmography-derived RR, IPI and EWS in respect to respiratory AEs and other SAE.

Related secondary endpoints are:

1. Incidence of RC markers recorded by the monitoring system during each Phase.
2. Incidence of respiratory AEs and SAE, number of ICU transfers and related length of stay, Code blues and RRT responses recorded in the two study Phases.
3. Average rate of early interventions for patient will be calculated in both study Phases. In Phase I there should only be non-alarm-triggered interventions, as in clinical practice, while in Phase II there should be two sub-groups of clinical early interventions: alarm-triggered and non-alarm-triggered.
4. Clinical staff's satisfaction related to the monitoring system's introduction in their current workflow will be evaluated through a survey performed at the end of the study.
5. Sensitivity and specificity of each monitored parameter in predicting and identifying respiratory AEs and SAE will be calculated. EWS will be the only parameter not automatically collected by the monitoring system but manually collected.

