## 8.8 Study Exit

Once the monitoring period has ended the patient will be treated according to the hospital clinical practice. The patient will exit the study upon their discharge from the hospital. Any adverse events (as defined in section 10) observed between the end of the monitoring period and study exit are reportable (as described in section 10.2). The Study Exit eCRF will be used to document that the patient has exited from the study. The reason for study exit will be captured on the Study Exit eCRF. The date of study exit, which should correspond to the date of discharge from the hospital will also be captured here.

If the study exit was for any reason other than normal study completion, refer to section 8.12 of the CIP, for appropriate Study Exit eCRF completion.

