### 7.9.2. Secondary Endpoints

The secondary endpoints are:

1. To compare phases in terms of Primary endpoint incidence;
2. To compare phases in terms of respiratory and SAE incidence, number of ICU transfers and related length of stay, Code blues and RRT responses.
3. To evaluate the rate of clinical early interventions performed by nurse staff to prevent a potential AE, introducing continuous monitoring devices connected to a remote monitoring platform;
4. To evaluate the nurses’ satisfaction related to the monitoring system introducing continuous monitoring devices connected to a remote monitoring platform;
5. To establish the Predictive values of  $\text{EtCO}_2$ , RR,  $\text{SpO}_2$ , plethysmography-derived RR, IPI and EWS in respect to respiratory and other SAE.

In order to evaluate secondary **endpoints #1 and #2**, the incidence of events will be reported together with the comparison between phases, by means of the Chi-square test or Fisher exact test for extreme

proportions, as appropriate. If the monitoring/study exposure results different between phases, also the rates of events will be reported, together with the 95% Poisson Confidence Intervals. The Poisson regression model will be used to calculate the Incidence Rate ratio (IRR), with the d-scale option.

For **endpoint #3**, the rate of clinical early interventions will be calculated as (number of early interventions)/(total time-person in FAS) and it will be reported together with the 95% Poisson Confidence Interval.

Early interventions include, as defined in CRF (Monitoring Period):

1. Stimulated subject to breathe;
2. Repositioned/opened airway;
3. Held or reduced Respiratory Depressive (RD);
4. Added or increased supplemental oxygen;
5. Ventilation support;
6. Other

**Endpoint #4** will be evaluated reporting a summary of the nurses' satisfaction answers.

To identify the predictive values for EtCO2, RR, SpO2, plethysmography-derived RR, IPI and EWS, which can predict respiratory and other SAE, a sensitivity analysis will be performed (**endpoint #5**), and the following parameters will be reported, for each RC marker:

1. **Sensitivity** = 
$$\frac{(\# \text{ of clinical events "Yes" and with RC marker "Yes"})}{(\# \text{ of clinical events "Yes"})} = \frac{TP}{(TP+FN)}$$
2. **PPV** = 
$$\frac{(\# \text{ of clinical events "Yes" and with RC marker "Yes"})}{(\# \text{ of events with RC marker "Yes"})} = \frac{TP}{(TP+FP)}$$

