RC marker	Clinical Events		Total
	Yes	No	
Yes	(TP)	(FP)	(TP + FP)
No	(FN)	(TN)	(FN + TN)
Total	(TP + FN)	(FP + TN)	(TP+TN+FP+FN)

To perform this analysis, a temporal window to find RC markers that could be associated with a clinical event will be defined (for example  $\pm 1$  minute from the event).

Due to the impossibility to identify the true negatives (TN), both the specificity and the NPV could not be calculated.

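### Endpoint #5 is meant to measure prediction, but its marker-event window is left open, the only example suits concurrent detection, and the sensitivity denominator is not limited to events with a valid signal

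*SAP*

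**What the plan says.** CIP 4.1.2 gives secondary objective 5 as characterising the predictive values of etCO2, RR, SpO2, plethysmography-derived RR, IPI and EWS. Its endpoint is wider than prediction: "Sensitivity and specificity of each monitored parameter in predicting and identifying respiratory AEs and SAE will be calculated".

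SAP 7.9.2 words the analysis as prediction. It looks for the parameters "which can predict respiratory and other SAE, a sensitivity analysis will be performed". Sensitivity is TP/(TP+FN), with all clinical events in the denominator. PPV is TP/(TP+FP). Specificity and NPV are dropped because true negatives cannot be identified.

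On linking markers to events, the SAP says that "a temporal window to find RC markers that could be associated with a clinical event will be defined". The only value it gives, marked as an example, is plus or minus one "minute from the event". It does not say when the window will be fixed, whether it should look backward only, or whether a marker is linked by its onset, by the time its criterion is met, or by overlap with the window.

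On the event period, CIP 8.1 collects adverse events from enrollment until study exit. CIP 8.8 places exit at hospital discharge and states that events "observed between the end of the monitoring period and study exit are reportable". CIP 8.7 starts monitoring on ward arrival and ends it at 72 hours at the latest. SAP 7.1.3 assigns endpoint #5 to both the FAS and the PPS, and the FAS keeps patients with short or poor-quality monitoring.

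**The concern.** A predictive claim needs the marker to come first. A window that is symmetric about the event and reaches back only one minute credits markers that follow the event and gives no credit to a warning that has already resolved. Those two errors act in opposite directions on sensitivity, so the net bias cannot be signed in advance.

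The denominator raises a separate problem. An event that occurs with no sensor attached tells us nothing about the sensor, but under the formula as written it would count against it. That biases sensitivity downward only.

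With specificity and NPV gone, the endpoint rests on sensitivity and PPV, and both move with the width and direction of the window. A window chosen after device and event data have been linked would leave the result open to selection.

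**Working it through.** The plan states no sensitivity, PPV or expected number of events for this endpoint, so there is no figure to reproduce. The check covers what the example window captures, and then which events can be hits at all.

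**1. Window geometry.** Put the event at time 0, with the window from −1 to +1 min (2 minutes wide). Take a marker that needs 3 minutes beyond threshold, which is the main branch for SpO2, RR and etCO2 in SAP 7.9.1.

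| Linking rule | Marker onset captured | 3-min criterion met at |
|---|---|---|
| Onset in window | −1 to +1 min | +2 to +4 min, always after the event |
| Criterion met in window | −4 to −2 min | −1 to +1 min |
| Overlap, 3-min episode | −4 to +1 min | −1 to +4 min |

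Under all three rules, an episode that ended before −1 min is not a true positive, and a marker first met after the event can be one. An episode still running at −1 min that met its criterion earlier counts only under the overlap rule.

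**2. Illustration of lead time.** The documents give no lead times. Assume an exponential lead from marker onset to event with mean m of 15 to 60 min. Percentages are shown for m = 60 and then m = 15.

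- ±1 min, onset rule, onset before the event: 1 − e^(−1/m) = 1.7% and 6.4%.
- ±1 min, criterion-met rule (lead 2 to 4 min): e^(−2/m) − e^(−4/m) = 0.967 − 0.936 = 3.2%, and 0.875 − 0.766 = 10.9%. About half of these have the criterion met after the event (lead 2 to 3 min: 1.6% and 5.6%).
- ±1 min, overlap rule, 3-min episode (lead up to 4 min): 1 − e^(−4/m) = 6.4% and 23.4%.
- Look-back of 60 min, used only as an example, with the criterion met before the event (lead 3 to 63 min): e^(−3/m) − e^(−63/m) = 0.951 − 0.350 = 60.1%, and 0.819 − 0.015 = 80.4%.

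**3. Events outside monitored time.** Written consent precedes surgery (CIP 8.4), and enrollment is complete once eligibility is also confirmed (CIP 8.5). Event collection can therefore begin before a device is attached, and under CIP 8.8 it runs past the end of monitoring. Assume a constant event rate over a stay of L days on the ward. The monitored share is monitored hours/(24 × L).

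- 72 h of monitoring: 72/120 = 60% at 5 days; 72/240 = 30% at 10 days.
- 24 h of monitoring: 24/120 = 20%; 24/240 = 10%.

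If unmonitored events stay in the denominator, these shares are ceilings on sensitivity even for a perfect marker. If events cluster early after surgery, the ceilings are higher. Restricting to events with a valid signal removes them.

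**4. The event period is inconsistent.** CIP 8.8 and the Study Exit column of CIP Table 2 extend event collection to discharge. SAP 5.1 keeps patients in the study for at most 72 hours, and SAP Table 1 has no Study Exit column. CIP 5 and 5.1 also retain the shorter period.

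**5. What exists to repair it.** SAP 7.1.3 already defines effective time with valid recorded data, but uses it for PPS entry and does not apply it to these events. CIP 10.2 records the date and time of each event, and CIP 8.10 makes device memory the source for the number and duration of markers.

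**The case against.** The strongest reply is that the window is explicitly still to be defined and ±1 minute is only an example, so no biased rule has been adopted. That is correct. What stands is that no predictive window or linking rule is prespecified, and the one illustration offered points away from prediction.

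A second reply is that the CIP endpoint covers identifying as well as predicting, and a near-event window is defensible for identification. This also stands. It is a reason to run two analyses.

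Four stronger readings are tempting and go beyond the documents.

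- A reader might infer that the SAP deliberately keeps unmonitored events. It does not say so. The inference comes from an unrestricted formula, use of the FAS and the CIP's collection period, while SAP 5.1 and Table 1 suggest a shorter period.
- A reader might infer that a 3-minute marker cannot fit a 2-minute window. That assumes full containment, which the SAP does not require, and it overlooks the SAP's branch for excursions under 3 minutes with an action taken.
- A reader might infer that every earlier warning is a miss. Under an overlap rule, an episode still in progress at −1 min is a hit.
- A reader might infer that EWS sensitivity must be near zero because observations are hours apart. The interval in CIP 3.1 ("spot checks performed at 4 to 6 hours intervals") describes usual-care SpO2 checks, not this study's EWS schedule. Vital signs are also likely to be taken when a patient deteriorates. In addition, the SAP applies the window to RC markers, and EWS is not one. The literature horizon that CIP 3.1 cites for EWS concerns cardiac arrest and death, so it is no yardstick for the marker window.

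**Conclusion.** The concern holds in a limited form. Endpoint #5 is worded as prediction, but the marker-event window and linking rule are not prespecified, and the only example would measure near-coincidence with the event. Applied as illustrated, it would miss resolved earlier warnings under any linking rule and could credit markers first met after onset. Separately, the sensitivity denominator carries no requirement for a valid signal. If events without one are counted, sensitivity is biased down.

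The documents do not fix the size. The captured shares (about 2% to 23% for ±1 minute, depending on the rule, against 60% to 80% for a 60-minute look-back) rest on assumed exponential lead times. The 30% to 60% ceiling rests on a constant event rate and an assumed 5 to 10 day stay.

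It would go too far to say that the study cannot support any early-warning conclusion, because the window can still be set properly. This is a secondary endpoint and the primary analysis is unaffected. The change should still be made before device and event data are linked.

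**What to change.** Amend SAP 7.9.2, endpoint #5, as follows.

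1. **Predicting.** Replace the symmetric window with a pre-event look-back. A true positive is a marker whose criterion is met before event onset, within a horizon fixed before device and event data are linked. Add one shorter and one longer horizon as sensitivity analyses.
2. **Identifying.** Report markers met at or after onset, or within a near-event window, in a separate table under that name.
3. **Linking rule.** State that the time at which the criterion is met governs the link, and use the same horizon to classify false positives for PPV.
4. **Denominator.** For each parameter, include only events with valid signal for that parameter in the look-back window, and report how many events are excluded. This also deals with etCO2 and apnea, which are not markers for PM1000N patients. Give manually collected EWS its own horizon, and state the cut-offs for EWS and IPI, which this endpoint currently lacks.
5. **Event period.** Reconcile SAP 5.1 and Table 1 with CIP Table 2 and CIP 8.8 (and CIP 5 and 5.1 with CIP 8.8).

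The cost is SAP wording and programming; event times and device memory are already collected. The price is fewer events in the analysis and so wider confidence intervals.

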Secondary Objective(s)	
The study secondary objectives are the following:
 

• To compare the two study Phases in terms of primary endpoint incidence.

• To compare the two study Phases in terms of respiratory AEs and SAE incidence, numbers of ICU transfers and related length of stay, Code blues and RRT responses.

• To evaluate the impact of introducing continuous monitoring devices connected to a remote monitoring platform, on the clinical workflow, defined as the rate of clinical early interventions performed by nurse staff to prevent a potential AE (e.g. patient stimulation, Jaw thrust maneuver, oxygen administration started or increased, medication change, etc.).

• To evaluate the impact of introducing continuous monitoring devices connected to a remote monitoring platform on clinical staff's workflow, defined as clinical staff's satisfaction related to the monitoring system.

• To characterize the predictive values of etCO2, RR, SpO2, plethysmography-derived RR, IPI and EWS in respect to respiratory AEs and other SAE.

 
Related secondary endpoints are:
 

• Incidence of RC markers recorded during each Phase.

• Incidence of respiratory AEs and SAE, number of ICU transfers and related length of stay, Code blues and RRT responses recorded in the two study Phases.

• Average rate of early interventions for patient will be calculated in both study Phases. In Phase I there should only be non- alarm-triggered interventions, as in clinical practice, while in Phase II there should be two sub-groups of clinical early interventions: alarm-triggered and non- alarm-triggered.

• Clinical staff's satisfaction related to each of the monitoring systems introduction in their current workflow will be evaluated through a survey performed at the end of the study.

	

• Sensitivity and specificity of each monitored parameter in predicting and identifying respiratory AEs and SAE will be calculated.

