## 12.3 Analysis of clinical data

Patient demographics and baseline characteristics will be presented using appropriate summary statistics. This includes mean and standard deviation, minimum, maximum and median with the interquartile range [IQR] for continuous variables and counts and percentages for categorical variables. Summary statistics will be reported with maximum 2 decimals, as appropriate. The SAS software (SAS Institute Inc., Cary, NC, USA) will be used to perform statistical analyses. Statistical tests will be based on a two-sided significance level of 0.05. Graphical representations will be used as deemed appropriate. No adjustments for multiple comparisons or multiple look at data will be performed. Outliers and influential observations will be identified via graphical plots and according to study team decision the analysis could be repeated excluding potential outliers. In case of missing data, no imputation method will be implemented for analysis.

The Full Analysis Set (FAS) will be used for primary final analysis. Any patient who does not satisfying the inclusion/exclusion criteria will be eliminate from the FAS population. Details of endpoints analyses and additional analysis will be described in the Statistical Analysis Plan. The analyses of primary objective on the proportion of patient with at least one RC markers will be reported together with their 95% confidence intervals and separately for each arm and phase of the study (see primary endpoint definition). When comparison of clinical primary outcomes is conducted the propensity score methods could be used to control for biases and confounding which may be due to the nature of this study. The

difference between the two groups within phase and between phases within groups will be analyzed by means of unpaired t-test or Mann-Whitney test according to the normal or non-normal distribution. For one secondary outcome the logistic regression model will be used to check potential predictors. Bivariate odds ratios (ORs) and 95% confidence intervals (95% CIs) will be estimated for each predictor. A multivariate logistic regression model will be performed according to univariate model's results. Other secondary outcomes will be performed using sensitivity and specificity analysis.

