## 4.2. Secondary Objectives

The study secondary objectives are the followings:

1. To compare the two study Phases (see Section 7.1.1) in terms of primary endpoint incidence;
2. To compare the two study Phases in terms of respiratory AEs and SAE incidence, numbers of ICU transfers and related length of stay, Code blues and RRT responses;
3. To evaluate the impact of introducing continuous monitoring devices connected to a remote monitoring platform on the clinical workflow, defined as the rate of clinical early interventions performed by nurse staff to prevent a potential AE (e.g. patient stimulation, Jaw thrust maneuver, oxygen administration started or increased, medication change, etc.);
4. To evaluate the impact of introducing continuous monitoring devices connected to a remote monitoring platform on clinical staff's workflow, defined as nurses' satisfaction related to the monitoring system;
5. To characterize the predictive values of EtCO2, RR, SpO2, plethysmography-derived RR, IPI and EWS in respect to respiratory and other SAE.

Related secondary objectives are:

1. Incidence of RC markers recorded by the monitoring system during each Phase;
2. Incidence of respiratory AEs and SAE, number of ICU transfers and related length of stay, Code blues and RRT responses recorded in the two study Phases;
3. Average rate of early interventions for patient will be calculated in both study Phases. In Phase I there should only be non- alarm-triggered interventions, as in clinical practice, while in Phase II there should be two sub-groups of clinical early interventions: alarm-triggered and non- alarm-triggered;
4. Clinical staff's satisfaction related to the monitoring system's introduction in their current workflow will be evaluated through a survey performed at the end of the study;
5. Sensitivity and specificity of each monitored parameter in predicting and identifying respiratory and SAE will be calculated. EWS will be the only parameter not automatically collected by the monitoring system but manually collected.

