## **7.12. Changes to Planned Analysis**

If the pre-defined cut-off of 24 hours of monitoring needed for the PPS will be unreachable, future modifications of this cut-off could be considered or, alternatively, a new definition of the populations could be done. Similarly, the 90% cut-off of time continuously monitored could change, accordingly to the study population, as appropriate.

Both the above changes could be applied in order to analyze the higher number of patients from the enrolled ones.

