### **10.1. Detection Tool**

The Detection Tool analyzes each patient's monitoring using an algorithm based on the device episodes thresholds as stated in the primary endpoint. The Detection Tool provides for each patient multiple Episodes. Since there could be multiple episodes in a short time period around each Episode, the Detection Tool is set to aggregate episodes with at most 30 minutes time difference between them in one file. In addition, the episodes file consists of time window of 30 min before and after the first and last episode.

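### SAP 7.9.2 withdraws the specificity promised for secondary endpoint #5 for a reason that depends on the unit of analysis, and gives IPI and EWS no positive/negative rule

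*SAP*

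**What the plan says.** The commitment appears in both documents. The protocol Synopsis, with the same commitment in 4.1.2, says: "Sensitivity and specificity of each monitored parameter in predicting and identifying respiratory AEs and SAE will be calculated". Protocol 12.3 adds: "Other secondary outcomes will be performed using sensitivity and specificity analysis". SAP 4.2 says: "Sensitivity and specificity of each monitored parameter in predicting and identifying respiratory and SAE will be calculated". The parameters named are EtCO2, RR, SpO2, plethysmography-derived RR, IPI and EWS.

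SAP 7.9.2 then sets out the analysis. It introduces the measures with "the following parameters will be reported, for each RC marker", gives formulas for sensitivity and PPV, and prints a 2x2 table that includes a true-negative cell. On timing it says only that "a temporal window to find RC markers that could be associated with a clinical event will be defined", with one minute either side of the event as an example. It closes with: "Due to the impossibility to identify the true negatives (TN), both the specificity and the NPV could not be calculated".

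RC markers (SAP 4.1 and 7.9.1) are built from SpO2, RR, EtCO2 and apnea. The Detection Tool (SAP 10.1) finds episodes "using an algorithm based on the device episodes thresholds as stated in the primary endpoint". Neither section mentions IPI or EWS.

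**The concern.** There are three linked problems.

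1. The SAP contradicts the protocol and its own section 4.2 on whether specificity will be reported, and the reason given is not a general one. PPV is kept, but PPV moves with the event rate and with the unit counted, so it cannot stand in for specificity.
2. IPI and EWS are named in the endpoint but are not RC markers. Nothing in the SAP says when either is positive, so a programmer following the text would produce no row for them.
3. The window is not fixed. The example is two-sided, so it admits markers that follow the event. It spans two minutes, while the duration criterion for three of the four markers is at least three minutes, and no overlap rule is given. Such a window suits identifying an event, not predicting one, and the endpoint asks for both. Leaving the choice open also allows it to be made after results are seen.

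At stake is whether the study can say how often a parameter is positive in patients who come to no harm, which bears directly on false alarms.

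**Working it through.** The documents state no sample size, power or precision for endpoint #5, so there is no planned figure to reproduce. The check has four parts.

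**1. Are the data for a true negative planned?** Device memory is the source for marker number and duration (Protocol 8.10). Time of event is recorded for AEs (Protocol 10.2). Potential episodes are derived for every patient (SAP 7.9.1, 10.1). A patient, or a fixed stretch of monitoring, with neither a positive reading nor an event can therefore be identified for the device parameters.

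**2. Illustrative counts.** Inputs: N = 182 evaluable (SAP 6); event rate 2–40%, an assumption borrowed from the range for postoperative pulmonary complications in Protocol 3.1, since no rate for the monitoring period is given; marker proportion 10% in event-free patients, an assumption based on SAP 6. With the whole patient as unit, TN = event-free patients − marker-positive event-free patients:

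- 2%: 182 − 4 = 178 event-free; TN = 178 − 18 = 160
- 10%: 182 − 18 = 164; TN = 164 − 16 = 148
- 40%: 182 − 73 = 109; TN = 109 − 11 = 98

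With fixed windows, 182 patients × 24 h = 4,368 person-hours, or 4,368 one-hour windows, each of which can be placed in one cell of the table.

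**3. Precision.** Exact (Clopper-Pearson) 95% intervals at an assumed specificity of about 80%, with every event-free patient eligible. One arm is 182/2 = 91. Phase II in one arm is 182 × 140/210 ÷ 2 ≈ 61. Phase I in one arm is 182 × 70/210 ÷ 2 ≈ 30.

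| Group | Event rate 2% | Event rate 40% | Half-width |
|---|---|---|---|
| Both arms (SpO2, EWS) | 142/178: 73.1–85.4% | 87/109: 71.1–86.9% | ±6–8 |
| One arm (EtCO2, capnography RR, plethysmography RR, IPI) | 71/89: 69.9–87.6% | 44/55: 67.0–89.6% | ±9–11 |
| One arm, Phase II | 48/60: 67.7–89.2% | 30/37: 64.8–92.0% | ±11–14 |
| One arm, Phase I | 23/29: 60.3–92.0% | 14/18: 52.4–93.6% | ±16–21 |

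Sensitivity, which the SAP keeps, at about 80% in both arms: 3/4 gives 19–99% (2% events), 14/18 gives 52–94% (10%), 58/73 gives 68–88% (40%). When events are few, the measure dropped is the better estimated one.

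**4. Dependence on unit and length.**

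- With a constant marker hazard, 80% specificity over 24 h becomes 0.8² = 64% over 48 h and 0.8³ = 51% over 72 h, so the length must be fixed.
- PPV = Se·π / [Se·π + (1 − Sp)(1 − π)]. With Se 80%, Sp 90% and π = 10% of patients, PPV = 0.08/(0.08 + 0.09) = 47%.
- If 12 windows per patient were counted instead, π = 0.10/12 = 0.83% and PPV = 0.00667/(0.00667 + 0.0992) = 6%.

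**The case against.** The strongest defence is that the SAP is open about the omission and right on its own terms: in continuous time, event-free and marker-free stretches have no natural count. The objective is worded as characterising predictive values, and sensitivity and PPV go part of the way. Protocol 12.2 lets deviations be justified in the final report, so the silence of SAP 7.12 on specificity is weak evidence of anything. This is a pilot and the endpoint is secondary. All of that stands, but it does not reconcile SAP 4.2 with 7.9.2, and it supplies no rule for IPI or EWS.

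It can also be said that the sentence in 7.9.2 names IPI and EWS as subjects of the analysis. That is fair: the firm defect is the missing positivity rule, and the absence of any result follows from the literal wording.

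Three stronger readings are tempting but unsupported.

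- A reader might take the counts of 160, 148 and 98 as a guaranteed minimum for a windowed table. They are not. Monitoring may end from 24 hours on mobilisation, or at ward discharge (Protocol 8.7), so some event-free patients may have no eligible window. If a quarter or a half of the 178 had none, about 134 or 89 would remain before positives are removed. The 10% is also a planning figure for the adjudicated RC endpoint; it does not bound unadjudicated status, IPI or NEWS.
- A reader might apply ±6–8 points to all parameters. It applies only to SpO2 and EWS.
- A reader might conclude that one particular windowed design is required. The documents show only that true negatives are countable; several designs would do.

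**Conclusion.** The point holds as a matter for correction before analysis. The two documents promise specificity, SAP 7.9.2 withdraws it, and the stated impossibility comes from the chosen unit and not from the data. As literally written, IPI and EWS receive neither sensitivity nor PPV, and the window is undefined.

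The precision in the table rests on assumed values: 80% specificity, event rates of 2–40%, 182 evaluable patients and full eligibility. It would be worse with fewer eligible windows. Specificity would be usable across both phases and wide in Phase I by device; sensitivity would be very imprecise if events are few.

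It would go too far to say that the SAP abandons endpoint #5: sensitivity and PPV for the RC markers remain.

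**What to change.** In SAP 7.9.2, replace the sentence on impossibility with a 2x2 table on a countable unit fixed before analysis. One suitable option is a fixed-length window per patient in which the marker precedes the event. In either case:

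- Count only events with onset during monitoring, because AEs are reportable up to discharge (Protocol 8.8) while markers exist only during monitoring.
- Report sensitivity, specificity, PPV and NPV with exact 95% CIs, by device where a parameter exists in one arm only.
- Use unadjudicated Detection Tool status for RC markers, because adjudication stops at the first RC per patient (SAP 7.9.1).
- Fix cut-offs for IPI and NEWS in advance. Candidate values appear in Protocol Appendix B (IPI) and Appendix E (NEWS). They would classify data for analysis only and set neither alarms nor care.
- Keep event-level sensitivity and PPV as supportive, with the window defined.

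If the sponsor prefers to leave specificity out, amend the Synopsis, Protocol 4.1.2 and 12.3, and SAP 4.2 to match 7.9.2. IPI, EWS and the window still need rules.

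The cost is SAP wording, new derivations for IPI and NEWS, and extra tables, with no new adjudication. The limitations to state are:

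- Under Protocol section 10 a marker with an action taken can itself become an AE, so marker and event overlap and sensitivity and PPV may be inflated. Report a version that excludes events defined only by a marker plus an action.
- Unadjudicated status includes clinically insignificant episodes (Protocol 8.7).
- Results depend on window length, and patients without an eligible window drop out.
- The documents give no measurement frequency for EWS, so its window may often hold no reading.
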